Cognitive behavioral therapy (CBT) is considered the gold-standard of empirically-based psychosocial treatments for depression (Cuijpers et al., 2013). Thus, CBT may serve as a useful, standardized foundation of psychosocial treatment to provide for patients with depression who are receiving psilocybin treatment. Additionally, psilocybin may help facilitate the uptake of CBT skills. Since psilocybin engenders greater cognitive flexibility and behavioral motivation (e.g., greater openness and social connectedness), it may help facilitate the uptake of CBT skills. Depressed individuals’ negative beliefs and unhelpful behaviors can become quite fixed, which can make treatment progress slow. Together, psilocybin may be a helpful catalyst for the cognitive and behavioral changes that are sought in CBT, and CBT may help to solidify cognitive and behavioral changes that are spurred by the psilocybin experience.

This study seeks to build on the current approaches to psilocybin treatment by combining CBT with the already-established psilocybin + PAT approach to (1) test whether CBT can be feasibly and acceptably added to the current psilocybin treatment modality and (2) to work towards protocolizing the psychosocial treatment that adjoins psilocybin drug therapy.

GENERAL INVESTIGATIONAL PLAN:

This study is a preliminary, proof-of-concept pilot to determine feasibility of the treatment methods and effect sizes. The study design is a single-group, fixed dose trial whereby 30 eligible participants will undergo 12 sessions of CBT during which two doses of psilocybin will be administered— a 10mg dose following the third session and a 25mg dose following the sixth session. Participants will be followed for an additional 3 months following treatment

termination. Study procedures will follow previously established safety guidelines (Johnson et al., 2008).

We hypothesize that psilocybin as an adjunct to 12 sessions of CBT will:

- (1) be feasible and reviewed favorably by participants, with minimal to no adverse effects;
- (2) Lead to reductions in negative thinking, increases in engagement with the environment, and improvements in depressive symptoms over the 7-month study period.

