The two drug administrations will be conducted with one individual participant at a time, each done in a single day. The first drug session (10mg dose) will be conducted over a 6-hour period and the second, high dose session (25mg) will be conducted over an 8-hour period. The first drug administration will be conducted following the third CBT session; the second will be conducted following the sixth session. Participants will be instructed to eat a light, low-fat breakfast on the day of the drug session and to arrive at the study site at 8am.

When the participant arrives at the UCLA Semel Institute for the drug session, prior to the psilocybin's administration, the participant will conduct a urine screen to test for the presence of and illicit drugs and, if the participant is biologically female, to confirm that she is not pregnant. Prior to the psilocybin's administration, participants will also be assessed for recent alcohol use through a breathalyzer test. Participants must have negative toxicology and pregnancy (if applicable) screens as well as no detectable amount of alcohol as measured by the breathalyzer test (i.e., 0.00% BAC) in order to proceed with the drug session. Participants who test positive for any illicit drugs, pregnancy, or alcohol will at any of the study screenings will not be allowed to proceed with the drug session and will be removed from the study. Participants will then be re-oriented to the plan for the day, including that they will be taking psilocybin and remaining in the therapy room for the duration of the drug experience (with the exception of bathroom breaks, as needed). The participant will then be given the psilocybin (10mg [administered in two 5mg capsules] for the first administration; 25mg [administered in one capsule] for the second administration) with a glass of water to begin the drug session. The results of the drug and pregnancy screens, administration of study drug(s), and safety measurements throughout the psilocybin session (see below) will all be catalogued on the study's case report form, which is shown in Appendix I (pg. 25).

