Following administration of the drug, the participant will lie down with an eyeshade over their eyes and given a pre-determined playlist of classical music to listen to through headphones (see music playlist in Appendix II, pgs. 26-28). Two therapists, termed drug monitors (i.e., the participant's assigned CBT clinician as well as a second clinician, ideally one male and one female) will remain present with the participant for the entirety of the 6–8-hour drug session. The monitors will check in with the participant every hour to (1) measure their blood pressure, with acceptable ranges not to exceed 140 systolic and 90 diastolic, and to (2) verbally check in on the participant's subjective well-being to ensure that the participant is not experiencing significant distress or in need of support (e.g., "Would you like to describe where you find yourself?").

Overall, participants will be encouraged to spend the drug session immersed in the drug's effects (as opposed to making conversation with the study clinicians), so that they can experience the drug's full effects and plan to discuss the experience in great detail in the therapy sessions. However, drug session monitors will be prepared to provide emotional support and, if necessary, physical support (e.g., holding the participant's hand) if the patient is distressed. Participants will be provided with a notepad to keep track of thought, emotions, and other experiences during the drug session should they choose to do so. Session monitors will also have notepad to write down experiences reported by the participants. After the drugs' effects have mostly subsided (i.e., at least 5 hours following the drug's administration), the participant will be asked to complete questionnaires, write notes about their experience, and complete a semi-structured interview with the study monitors.

After the effects of the psilocybin have resolved (at least 6 hours following administration), the participant will be released into the care of an identified support person. In order for the participant to be released following a psilocybin session, he/she must be oriented to person, place, time, and situation; have successfully completed the post-drug session clinical interview and questionnaires; not be experiencing acute distress (e.g., suicidal ideation) that requires

psychiatric attention; and have blood pressure and heart rate measurements within normal ranges.

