The main effects of psilocybin are psychological. A high dose of psilocybin, which participants would receive in this study, can bring about a very broad range of profound changes in perception and consciousness during the hours of drug action. About one-third of people in our previous study reported moderate to strong feelings of fear or anxiety after receiving psilocybin. Changes in normal perception can include visual or hearing changes (pseudo-hallucinations), and unusual smells, tastes, or other bodily sensations. Participants may experience anxiety, panic, or paranoia (suspiciousness) during the period of drug action. Participants may behave in ways such as intense crying, laughing, or panic that participants might later find embarrassing. Participants may experience powerful emotions, both pleasant and unpleasant. Participants' sense of time may be altered, such that time seems to pass more quickly or slowly than usual. Participants may have a sense that the participant's body and mind have separated. The effects of psilocybin usually last about 5-7 hours.

As with other experiences of a strongly positive or negative nature, participants may have dreams and/or lasting memories of psilocybin session experiences. After the psilocybin session, there may be short-term to permanent changes in personality, attitude, or creativity.

During the period of drug action, psilocybin may also cause dizziness, nausea, vomiting, incontinence, increased pulse and blood pressure, dilated pupils, increased reflexes, tremors, and muscle twitching. A few people in an earlier study had blood pressure increases during

psilocybin sessions. Taking any drug also involves a possibility of allergic reactions such as itching, rash, or hives. Some people have reported headache starting about 7 hours after taking psilocybin and sometimes lasting into the following day. Some participants have reported leg pain lasting 1-2 days after the session.

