stress-reduction techniques, including leading relaxation exercises and providing reassurance to participants as needed. Before drug administration, hourly for the first four hours, and before discharge from the drug session blood pressure will be measured. Participant's experience of headaches and adverse visual-perceptual effects will be elicited at the end-of-drug session. Additionally, at each participant-contact (i.e., each CBT session and study assessment), a study therapist/assessor will inquire about any persisting headaches and/or visual-perceptual effects. Participants will be asked about any somatic symptoms and sensory experiences (i.e., visual, auditory, tactile, olfactory, gustatory) that have continued since the psilocybin's effects have subsided. Participants with persisting headache and/or persisting visual-perceptual effects that meet DSM-5 criteria for hallucinogen persisting perception disorder will be further assessed by a study psychiatrist to determine whether pharmacological treatment is indicated. Participants will also be asked about any alcohol use in the 24 hours following the psilocybin session.

A study psychiatrist will be onsite and available within 15 minutes for the entire duration of each drug session for an emergency and to administer rescue medication(s) as necessary.

Heart rate and blood pressure will be recorded at study's baseline screening assessment (averaged across 4 separate measurements). Heart rate and blood pressure will be re-recorded on the morning of the psilocybin drug session and monitored at hourly intervals following drug administration from 60 to 360 minutes. Heart rate and blood pressure will be taken prior to participant's discharge from the psilocybin drug session as well. Each participant's vital sign measurements and administration will be logged on the study case report form (see attached in Appendix I; pg. 25). In case of a medical emergency, the follow procedures will be followed:

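### After the 10 mg session, a delayed headache that clears before the next visit is never asked about by name and may be under-recorded

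*Combined protocol and SAP*

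**What the plan says.** **Expected reaction.** Section 1 (Potential Risks) states: "Some people have reported headache starting about 7 hours after taking psilocybin and sometimes lasting into the following day". The same paragraph mentions leg pain with a duration of one to two days.

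**Session day.** Section 3 (Safety Measures) says the participant's "experience of headaches and adverse visual-perceptual effects will be elicited at the end-of-drug session". The General Investigational Plan sets the length of the sessions: "The first drug session (10mg dose) will be conducted over a 6-hour period", while the "high dose session (25mg) will be conducted over an 8-hour period". It also sets the earliest release: "After the effects of the psilocybin have resolved (at least 6 hours following administration), the participant will be released".

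**Later contacts, by name.** Safety Measures adds that at each CBT session and study assessment a therapist or assessor "will inquire about any persisting headaches and/or visual-perceptual effects". The accompanying question on bodily and sensory symptoms is limited to those still going on after the drug has worn off.

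**Later contacts, in general.** The General Investigational Plan, Potential Risks and a later part of Safety Measures all have the clinician ask at the next CBT session about effects that are persisting or adverse. Safety Measures extends this to every remaining session and assessment, and its examples are flashbacks and recurrent psychotic experiences. Participants also leave each session with a number to call.

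**Use of the data.** The first hypothesis in the General Investigational Plan is that the treatment will "be feasible and reviewed favorably by participants, with minimal to no adverse effects".

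**The concern.** The protocol singles out headache as worth asking about directly, and it states when headache tends to start. The direct question on the day of the 10 mg dose nevertheless falls before that time. The direct question at later visits is worded so that a headache already over does not qualify. Between the two lies the course the risk section itself describes: onset in the late afternoon or evening of the dosing day and resolution that night or the next day.

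The tolerability part of the first hypothesis is at stake. This is a single-group pilot of 30 with no control arm, so the adverse-effect description rests on simple counts. Under-recording moves those counts in one direction, towards the hypothesis. It also makes capture depend on how each clinician phrases a general question, because the protocol gives two instructions of different scope for the same visit.

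**Working it through.** **Inputs**
- Stated headache onset: about 7 h after dosing (Potential Risks).
- Session lengths: 6 h for 10 mg and 8 h for 25 mg (General Investigational Plan).
- Earliest release: 6 h after dosing, as a minimum (General Investigational Plan).
- Ideal clock times for the 10 mg session: dose 9:00, questionnaires 2:00 pm, discharge 3:00 pm (Appendix I, Case Report Form).
- Next contact: no more than a couple of days after the session. I take 24 to 72 h as an assumed range.

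**Step 1: reproduce the session length.** Discharge 15:00 − dose 9:00 = 6 h. This agrees with the stated 6-hour session and with the minimum release time.

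**Step 2: time of the end-of-session question against stated onset.** Margin = time of question − 7 h. A negative value means the question comes before the stated onset.

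| Session and reading | Question, h after dose | Margin |
|---|---|---|
| 10 mg, asked at discharge | 6 | 6 − 7 = −1 h |
| 10 mg, asked with the questionnaires | 5 | 5 − 7 = −2 h |
| 25 mg, 8 h counted from dosing | 8 | 8 − 7 = +1 h |
| 25 mg, released at the 6 h minimum | 6 | 6 − 7 = −1 h |

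The 10 mg form counts its 6 hours from dosing, which suggests the same convention at 25 mg. No 25 mg form is in the documents, so this cannot be confirmed.

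**Step 3: is such a headache still present at the next visit?** With a 9:00 dose, onset is at 9:00 + 7 h = 16:00, one hour after the ideal discharge time.
- If it ends the same evening, it is over by midnight, 24 − 9 = 15 h after dosing, and so before any visit at 24 h or later.
- If it runs into the following day, it ends between 15 h and 15 + 24 = 39 h after dosing. It is over by a visit at 48 to 72 h, but may still be present at a 24 h visit.

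**Step 4: which questions reach a headache that has ended?**

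| Question | Names headache? | Reaches a resolved, delayed headache after 10 mg? |
|---|---|---|
| End of session | Yes | No, if asked at the nominal time |
| Later headache question | Yes | No, persisting only |
| Later bodily-symptom question | No | No, continuing only |
| General inquiry at CBT visits | No | Yes, if the participant mentions it |
| Participant's own call | No | Yes, if the participant calls |

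Leg pain is in a weaker position still: no question names it, and the bodily-symptom question covers it only while it continues.

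**Step 5: size.** The documents give no headache rate and no distribution of onset or duration, so no expected number can be derived. The scale is 1/30 = 3.3 percentage points for each participant whose headache goes unrecorded, if all 30 are dosed.

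**The case against.** The strongest reply is that the protocol already asks. The general inquiry is required at a fixed visit shortly after each session and repeated at every later contact, and events are documented and reported. A headache that came and went is an adverse effect within that question. Participants are also told of the listed side effects at consent. This stands: a reader might infer that later contacts ask about persisting headache and nothing else, so that the event is missed, and the documents do not support that. What remains is that the general question does not prompt for headache, and the only examples attached to it are psychological or perceptual.

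The timing is also softer than clock subtraction implies. Six hours is a minimum, the form's times are ideal ones beside a column for actual times, participants can be kept longer, and an onset of about 7 hours in some people is a loose description. So the 10 mg question is nominally, not invariably, too early, and some headaches will have begun by then.

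Three further inferences are tempting and do not hold:
- **A biased comparison between doses.** The Statistical Analysis Plan section plans no comparison of adverse events by dose, and dose is inseparable from order and CBT exposure in any case.
- **A withdrawal rule that cannot be applied.** The rule on headache lasting more than two days after the first dose concerns a headache that the persisting-headache question is suited to find. The transient headache at issue here would not meet it.
- **Proof that onset and duration go unrecorded.** Only the 10 mg session form is reproduced; the follow-up forms are not, so their content is unknown.

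**Conclusion.** The point holds in a limited form. After the 10 mg session, a delayed headache that has resolved by the next visit is not covered by any question that names headache, and its capture depends on a general inquiry or an unprompted call. At 25 mg the gap is uncertain: absent if the 8 hours run from dosing, present if release is near 6 hours.

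The likely consequence is some under-recording of an expected and usually short-lived reaction, in the direction that favours the tolerability hypothesis. Its size cannot be stated. It does not touch the planned analyses of retention, satisfaction, HAM-D or GAF. The conclusion rests on the protocol's own onset time, on the end-of-session question being asked near the nominal time, and on the next visit usually falling after the headache has ended. It is worth correcting because the correction is cheap, not because the trial's conclusions are in danger.

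**What to change.** Reconcile the headache wording in Safety Measures with the onset described in Potential Risks and with the general inquiry in the General Investigational Plan, Potential Risks and Safety Measures:

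- At the first CBT visit after each psilocybin session, ask by name about headache, leg pain and visual-perceptual effects at any time since dosing, including any that have resolved.
- Record onset and end time for each.
- Keep the end-of-session question and the persisting-effects questions at later contacts.
- When these events are tabulated, use the same post-dose window for both sessions.

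The cost is a reworded question and two time fields for each event reported, at a visit already scheduled, with no added visit. Reported adverse-effect counts will be somewhat higher. No dose, session length, release criterion or withdrawal rule needs to change for this.

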Participants will be instructed not to drive an automobile or engage in any other potentially dangerous activity for the remainder of the day. The study staff will also orient the identified support person to whom the participant is being released to be available to provide emotional support, if necessary, but also to provide space if the participant would rather be alone. Each participant will be given one of the study clinician's direct pager/cellphone number to call if he/she needs support prior to their next CBT session. Within a couple of days following the drug session, participants will conduct their next weekly session of CBT, where the study clinician will inquire about any persisting or adverse effects of the psilocybin.

PARTICIPANTS:

Participants will be adults (ages 21-60) who meet current criteria for major depressive disorder.

STUDY INCLUSION AND EXCLUSION CRITERIA:

All participants must meet the following inclusion criteria to be eligible for the study:

- Ages 21-60,
- Able to swallow capsules,
- Patients with a current major depressive episode or a history of major depressive episodes based on the DSM-5 criteria (American Psychiatric Association, 2013),
- Active current depressive symptoms (i.e., scores >16 on the Hamilton-Depression Rating Scale covering the prior 2 weeks; Hamilton, 1986),
- Have an identified support person who can pick up the individual from UCLA Semel Institute and drive individual home following psilocybin sessions,
- For women of child-bearing potential – using one form of highly effective contraception (e.g., oral contraceptive pill) and willingness to continue contraceptive use for duration of study. Must be willing to take on-site pregnancy tests.
- Agree to refrain from any psychoactive drug (including alcohol) within 24 hours of each drug session and during the drug sessions. Participants will be allowed to consume their usual amount of caffeine prior to and after the drug sessions.
- Agree to not take any PRN medications on the mornings of the drug sessions
- Patient has been medically cleared for the study by a physician
- Participants must remain on anti-hypertensive medications if prescribed previously to manage hypertension

Participants will not be enrolled in the study if they meet any of the following exclusion criteria:

- A personal or family history (first or second-degree) of psychosis or bipolar disorder

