Each participant will undergo a physical screening by a qualified health practitioner at UCLA's Clinical and Translational Research Center (CTRC). The physical screening will include a general physical exam (i.e., recording participant's blood pressure, pulse, height, and weight, and conducting non-invasive check of heart, lungs, ear/nose/throat, and reflexes). Since psilocybin can increase pulse and blood pressure (Griffiths et al., 2006; Johnson et al., 2008), patients with resting blood pressure above 140 systolic, 90 diastolic or heart rate > 90 beats per minute (averaged across four separate measurements within the screening process) will be excluded. The physical screening will also include an electrocardiogram (ECG) and a 30-cc blood draw for a complete blood count (CBC), a metabolic panel, a thyroid-stimulating hormone (TSH) test, liver functioning tests, and a C-reactive protein (CRP) blood test. Finally, the physical screening will include a urine drug screen to determine any current drug use and a urine pregnancy screen to rule out pregnancy in females.

In addition to the physical screen at the UCLA Clinical Trial Research Center (CTRC), the participant will undergo a medical interview with a study assessor. The study assessor will inquire about and record the participant's current medical conditions and medication use. Medications taken by the participants (both prescribed and over the counter) will be recorded, including SSRIs or any other serotonergic-acting drug (e.g., St. John's Wort). Chronic and/or recent use of antidepressants (e.g., serotonin reuptake inhibitors) and other substances that affect serotonergic functioning can attenuate the effects of hallucinogens (Bonson, 2012; Strassman, 1992), and thus pose a scientific confound. For eligible participants with prior exposure to a drug with serotonergic activity, the serotonergic-acting drug will need to have been discontinued for at least five half-lives of active major metabolites prior to psilocybin exposure. Participants will not be able to proceed past the study screening if/while they are currently on serotonergic

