patients with mood disorders. [name] is a licensed clinical psychologist. She has extensive training from her graduate and postdoctoral training in the psychosocial treatment of mood, psychotic, and anxiety disorders. Both in her work at UCLA and her private practice, she specializes in cognitive-behavioral therapy for these disorders. Additionally, Drs. [name] and [name] have taken a Psychedelic Assisted Psychotherapy (PAT) course that was being delivered at a Los Angeles-based counseling center (Maple Counseling). The course is a 7-part course that includes the fundamentals of PAT as well as safety and ethical considerations when delivering PAT.

Prior to Drug Sessions: All participants are fully informed of the side effects that they might experience. Multiple entrance criteria and study protocols have been put in place to ensure safety of participants, including a detailed medical history screening and blood pressure readings at four times on at least two days prior to the drug administration. Participants with resting blood pressure exceeding 140 systolic and 90 diastolic (mmHg) averaged across their four readings will be withdrawn from the study. Further, to avoid risk of a serotonin syndrome reaction (Callaway & [name], 1998), we will exclude participants who are currently taking any medications that affect serotonergic functioning, including serotonin reuptake inhibitors as well as over the counter supplements such as St. John's Wort. For eligible participants with prior exposure to a drug with serotonergic activity, the serotonergic-acting drug will need to have been discontinued for at least five half-lives of active major metabolites prior to psilocybin exposure.

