Participant Education:

- All participants will be informed of the possible side effects and risks previously mentioned through the informed consent form and discussions with study psychologists and research staff.

Consent Procedures:

- Participants will provide informed consent to screening and all study procedures prior to study entrance.

Participant Monitoring and Removal from the Study:

- The research team will continually assess the participant's health throughout the study and will remove participants from the study if physical or mental deterioration is observed.
- Immediate removal from the study will result if significant adverse reaction to psilocybin or assessment procedure is noted.
- Upon removal of a participant from the study, he or she will be provided with the appropriate follow-up treatment by the study physician.

3. SAFETY MEASURES:

Two drug session monitors will be present for the entire drug session. One of the monitors will be the participant's assigned clinician for the psychotherapy. A second monitor will be present to help with the drug session and ensure that the participant will never be alone if the primary monitor needs to step out (e.g., to use the restroom). Both session monitors will be psychologists and/or psychiatrists. These clinicians will receive didactic training in psychedelic-assisted therapy (PAT; see above). They will also have extensive experience with both mood and psychotic disorders and be experienced in managing acute distress in patients through various

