Participant Monitoring and Removal from the Study:

Noncompliance. Participants will be withdrawn from the protocol if they are noncompliant with the study procedures (for example, missing 2 or more consecutive CBT without calling ahead; refuse to participate in follow-up interviews).

Failing the medical or psychological screening. Participants will be withdrawn from the study if any of the following are evidenced during the medical screen or psychological screen, or if any of the following are elucidated during study:

- A personal or family history (first or second-degree) of psychosis or bipolar disorder
- Resting blood pressure above 140 systolic, 90 diastolic or heart rate > 90 beats per minute (averaged across four separate measurements)

- Meeting criteria for a DSM-5 cluster B personality disorder (narcissistic, histrionic, borderline, antisocial personality disorder),
- Active suicidality (i.e., HAM-D item 3 score of 3 or greater) or other psychiatric disturbance requiring acute treatment
- Current use of antidepressants, other serotonergic-affecting substances (e.g., St. John's Wort and 5-hydroxytryptophan), lithium, or efavirenz [regardless of whether the drug(s) is/are prescribed for MDD or other conditions]
- Current use of opioids (e.g., codeine, fentanyl, hydrocodone, meperidine, tramadol)
- Currently receiving cognitive behavioral therapy,
- Any of the following cardiovascular conditions: uncontrolled hypertension, coronary artery disease, congenital long QT syndrome, cardiac hypertrophy, cardiac ischemia, congestive heart failure, myocardial infarction, tachycardia, artificial heart valve, a clinically significant screening ECG abnormality, or any other significant cardiovascular condition
- QTc interval measurement of > 450 ms in males or > 460 ms in females as measured by the baseline ECG
- A history of stroke or Transient Ischemic Attack (TIA)
- Epilepsy or history of seizures
- Insulin-dependent diabetes
- Meeting criteria for a DSM-5 substance abuse or dependence within prior 6 months (including for nicotine and cannabis)
- Positive urine drug screen for illicit substances (excluding cannabis)
- Use of other psychedelics or ketamine within prior 12 months
- Adverse prior reaction to a psychedelic agent
- Pregnant, trying to get pregnant, or nursing

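### Blood pressure and heart rate are re-recorded on each dosing morning, but no limit or action is tied to that reading

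*Combined protocol and SAP*

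**What the plan says.** **Dosing morning.** 3. SAFETY MEASURES: "Heart rate and blood pressure will be re-recorded on the morning of the psilocybin drug session". The sentence gives no limit and no action. The averaging over four measurements in that paragraph belongs to the baseline screening assessment.

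**Conditions to proceed.** GENERAL INVESTIGATIONAL PLAN: "Participants must have negative toxicology and pregnancy (if applicable) screens as well as no detectable amount of alcohol". Blood pressure and heart rate are not listed. In Appendix I, the required-value lines on the 10 mg form cover symptoms, antihypertensive intake, pregnancy, drug test, alcohol, cannabis and as-needed medication. None covers blood pressure or heart rate. The 25 mg form is not shown.

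**During the session.** The same plan section gives a blood pressure range for the hourly checks after dosing, "with acceptable ranges not to exceed 140 systolic and 90 diastolic", and states no action if it is exceeded.

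**Entry limit.** Resting pressure above 140 systolic or 90 diastolic, or heart rate above 90, excludes. SCREENING AND TESTING PROCEDURES defines this as "averaged across four separate measurements within the screening process". The paragraph headed Prior to Drug Sessions places the four readings on at least two days before dosing and says that participants with "resting blood pressure exceeding 140 systolic and 90 diastolic (mmHg) averaged across their four readings will be withdrawn from the study". That sentence joins the two pressures with 'and' and leaves out heart rate, unlike the criteria lists.

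**After entry.** Under 3. SAFETY MEASURES, Participant Monitoring and Removal from the Study, the same numeric item is in a list that applies at screening or "if any of the following are elucidated during study". Participants who have begun CBT then stay in the study but receive no further psilocybin.

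**The concern.** The protocol explains its entry limits by noting that psilocybin can raise pulse and blood pressure. On that reasoning the reading that matters most is the one taken just before the drug is given. It is collected, but staff are not told what to do with it.

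Consider a participant who averaged 138/88 at screening and reads 146/92 on the morning. That is above the entry limit, and above the range set for the hourly checks, before the drug has acted. The plan does not say whether to repeat the reading, wait, postpone, withdraw or dose, so different monitors could act differently. At stake are participant safety and consistent conduct across sessions. The efficacy analysis is not affected.

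**Working it through.** **1. Which rule reaches a raised pre-dose reading?** The plan states no figure for this, so the rules are set side by side.

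| Rule | Value | Reaches the dosing-morning reading? |
|---|---|---|
| Conditions to proceed (GENERAL INVESTIGATIONAL PLAN) | None for BP or HR | No |
| 10 mg session form (Appendix I) | None for BP or HR | No |
| Hourly range (GENERAL INVESTIGATIONAL PLAN) | 140/90 | No: post-dose, no action stated |
| Acute hypertension (3. SAFETY MEASURES) | Closer monitoring above 160 or 100; physician notified if above 160/100 for four 15-minute intervals, or at 220/120 | Not a rule for withholding a dose; 146/92 is below every trigger |
| Tachycardia (3. SAFETY MEASURES) | Rechecks above 120; physician notified above 150 | Not a rule for withholding a dose |
| Adverse drug reaction (3. SAFETY MEASURES) | Rescue medication for BP exceeding 160/100 in session 1 | Stops dose 2 only, on session 1 events |
| Withdrawal list (3. SAFETY MEASURES) | Mean of four above 140/90, or HR above 90 | Unclear: see step 2 |

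By contrast, discharge after a session does require blood pressure and heart rate within normal ranges.

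**2. Does the withdrawal list close the gap?** Only in part. Its limit is a mean of four measurements, and the two places that say when those are taken put them in screening or on at least two days before dosing. No repeat readings are required on the morning, so one reading of 146/92 does not meet the criterion as written. If four morning readings did average 146/92, the only stated result is loss of all later psilocybin sessions, for what may be a transient rise.

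**3. How old is the screening average?** With weekly sessions, session 1 to session 3 is 2 weeks. Session 1 to session 6 is 5 weeks, and to session 7 is 6 weeks; the protocol gives both positions for the 25 mg dose. The average is therefore at least about 2 weeks old at 10 mg and 5 to 6 weeks old at 25 mg.

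**4. How often would a rule at the protocol's own limits trigger?** Planned mornings: 30 × 2 = 60. The documents give no blood pressure or heart rate distribution, so every input below is assumed.

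- BP means 118/75, 122/77 and 126/79; between-person SD 11/8 or 12/9; within-person SD 8/5 or 10/7; systolic–diastolic correlation 0.65 between and 0.5 within persons.
- HR mean 68–76, between-person SD 8–10, within-person SD 5–7.
- Screening: two readings on each of two days, passing if the mean is within the limits. Dosing morning: mean of four readings.
- The within-person SD of a same-day mean of four is s × √[(1 + 3ρ)/4], where ρ is the same-day correlation. For s = 8 this is 4.0 at ρ = 0 and 8 × √(3.1/4) = 7.0 at ρ = 0.7.

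Simulated probability of a morning mean above the limit, given a pass at screening:

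| | ρ = 0 | ρ = 0.5 | ρ = 0.7 |
|---|---|---|---|
| BP above 140 or 90 | 2.2%–7.9% | 4.1%–12.7% | 4.8%–14.3% |
| × 60 mornings | 1.3–4.7 | 2.4–7.6 | 2.9–8.6 |
| HR above 90 | 0.2%–3.4% | not run | 0.6%–6.4% |
| × 60 mornings | 0.1–2.0 | not run | 0.3–3.8 |

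A single reading would trigger the BP limit on 5.8%–16.5% of mornings. A single reading above 160 or 100 occurs on 0.07%–1.08% of mornings, or 0.04–0.65 of 60. Most holds would be for modest elevations.

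**The case against.** The strongest objection is that the protocol already carries a numeric limit past screening. The withdrawal list applies 140/90 and heart rate 90 if found during the study, and those already in CBT then get no more psilocybin. That stands. A reader might infer from the silence about the dosing morning that no stated value can ever stop a dose, or that the protocol hands the decision to staff judgement. The documents support neither. A qualifying four-measurement mean does bar dosing, and no text grants discretion over the morning reading; the text is silent. What remains open is how the limit applies to that reading and whether anything short of a bar is available.

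A second objection is that other safeguards limit the consequences. Antihypertensives must have been taken as prescribed, the form requires no unusual physical symptom or stress, and a psychiatrist is on site and available within 15 minutes. There are escalation steps, and the team "will remove participants from the study if physical or mental deterioration is observed". These are real protections and keep the point from being a critical hazard. None gives a value for the pre-dose reading, and at 146/92 none requires physician contact.

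A third objection is that the simulated percentages describe how often a new rule would trigger, not how often an unsafe dose would be given. That is correct, and they are used here only to cost the change.

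**Conclusion.** The point holds in this form: the plan takes a pre-dose reading and ties no limit or action to it, and the one numeric rule that continues after entry neither clearly covers that reading nor allows a hold short of barring later sessions. Someone above the trial's own entry limit can therefore be dosed under the plan as written, without a required call to a physician.

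This rests on the text alone and applies to all 60 planned mornings. It is a low-cost safety improvement. The estimate of roughly 1 to 9 blood pressure holds in 60 depends wholly on the assumed distributions and same-day correlation, and no estimate of harm prevented can be drawn from the documents.

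**What to change.** 1. In the conditions to proceed (GENERAL INVESTIGATIONAL PLAN), and as a required entry on both session forms: give the capsule only if resting pre-dose pressure, averaged over repeat readings between 8:00 and 9:00, is ≤140 systolic and ≤90 diastolic, with heart rate ≤90. Otherwise hold the dose, notify the study physician and reschedule.
2. In the withdrawal rules, state that a raised dosing-morning average leads first to hold and reschedule. The bar on psilocybin applies if the average is still raised on the rescheduled day, or if the physician finds uncontrolled hypertension or tachycardia. The participant stays in CBT and assessments. Without this step, item 1 would say reschedule where the current list says withdraw.
3. Set the rescheduling window so that the integration session still follows the dose as planned: "Within a couple of days following the drug session, participants will conduct their next weekly session of CBT".
4. Align Prior to Drug Sessions with the criteria lists: SBP >140 or DBP >90 mmHg, or HR >90 bpm, averaged across four readings.
5. State what is done when the hourly 140/90 range is exceeded, or refer to the acute hypertension steps.

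The cost is protocol wording and one line per form; the readings fit in the hour already scheduled before dosing. The real burden is the postponed sessions. Each takes a second day from the participant and two monitors and moves the following integration session. For a participant whose four morning readings average above the limit, item 2 relaxes the current text, since one raised morning would no longer end psilocybin dosing.
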